HRPP	Human Research Protections Program
Ig	Immunoglobulin
IRB	Institutional review board
LISB	Laboratory of Immune System Biology
MDCK	Madin Darby Canine Kidney
NCBI	National Center for Biotechnology Information
NIAID	National Institute of Allergy and Infectious Diseases
NIH	National Institutes of Health
PBMC	Peripheral blood mononuclear cell
PI	Principal investigator
RNA	Ribonucleic acid
RNA-seq	RNA sequencing
SAE	Serious adverse event
SARS-CoV-2	Severe acute respiratory syndrome coronavirus 2
SRA	Sequence Read Archive
TBNK	T, B, and natural killer (cells)
TDaP	Tetanus, diphtheria, and pertussis (vaccine)
UP	Unanticipated problem
USPHS	United States Public Health Service

Protocol Summary

- Short Title:** Immune response to flu vaccine
- Sample Size:** N=170 (n=24 subjects enrolled in year 1; targeting up to n=120 new subjects in year 2 and n=7 new subjects per year for years 3-5)
- Accrual Ceiling:** N=300
- Study Population:** Healthy volunteers aged 18 years and older (no upper age limit)
- Accrual Period:** 5 years (enrollment open August through February each year)
- Study Design:** This is an open-label, prospective, exploratory study to assess the baseline and post-vaccination immune responses of healthy volunteers to an approved seasonal influenza vaccine. Subjects will undergo baseline blood collections on day -7 and on day 0 before receiving the study vaccine. After vaccination, blood will be collected on days 1, 7, 14, 28, 70, and 100. Optionally, subjects may also give blood once a month, as requested, up until 1 year after vaccination. Research evaluations will include vaccine antibody titers. Additional evaluations may include peripheral immune cell phenotyping, RNA sequencing (RNA-seq) of whole blood and defined peripheral blood cell subsets, and measurement of serum proteins and antibodies. Subjects may optionally provide stool samples at some visits for exploratory microbiome assessments. Additionally, subjects may optionally continue study participation annually through the 2023-24 influenza season.
- Study Agent Description:** An approved inactivated seasonal influenza vaccine administered once by intramuscular injection. The study vaccine will be the vaccine stocked by the NIH pharmacy, either Flucelvax Quadrivalent or Fluvirin (Seqirus Inc.) for subjects under 65 years, or Fluzone High-Dose (Sanofi Pasteur) for subjects 65 years and older.
- Primary Objective:** Identify baseline correlates of immune response to the seasonal influenza vaccine in healthy individuals
- Secondary Objectives:** Validate the findings of prior study 09-H-0239 (“Cellular and Molecular Characterization of the Immune Response in Healthy

NIH Employees at Baseline, and After Immunization with the H1N1 or Seasonal Influenza Vaccines”), specifically the relationship between cell populations and/or gene transcripts at baseline and after vaccination that correlate with vaccine immune response

Evaluate the effect of prior severe acute respiratory syndrome coronavirus 2 (SARS-CoV-2) infection on the antibody response to the seasonal influenza vaccine in healthy volunteers

Primary Endpoint: Change in antibody titer response to vaccination, as measured by microneutralization titers at day 0 and day 70 and its relationship with novel baseline biomarkers

Secondary Endpoint: Change in antibody titer response to vaccination, as measured by microneutralization titers at day 0 and day 70 and its relationship with established baseline biomarkers (CD38⁺ CD20⁺ B cell frequencies and/or transcriptomic signatures) and post-vaccination biomarkers (plasmablast cell frequencies and/or transcriptomic signatures)

Difference in antibody titer response to vaccination between subjects with a history of symptomatic or asymptomatic SARS-CoV-2 infection and those with no evidence of SARS-CoV-2 infection

Précis

Certain functions of the immune system are revealed only when the immune system is challenged. When a person is vaccinated, a coordinated response results: activation and interaction of distinct innate and adaptive immune cell populations and pathways, culminating in the formation of germinal centers from which antibody-producing plasma cells and memory B cells derive. By taking measurements at various time points before and after vaccination, we can build a comprehensive picture of how the immune system responds to a vaccine challenge. The seasonal influenza vaccination provides an excellent model of coordinated immune activity involving innate and adaptive responses, as demonstrated in a past NIH study in 2009-2011; however, scientific advances and the possibility of multi-season responses in individuals warrant a new follow-up study with more comprehensive sampling.

This is an open-label, prospective, exploratory study to assess the baseline and post-vaccination immune responses of healthy volunteers to an approved seasonal influenza vaccine. Subjects will undergo baseline blood collections on day -7 and on day 0 before receiving the study vaccine. After vaccination, blood will be collected on days 1, 7, 14, 28, 70, and 100. Optionally, subjects may also give blood once a month, as requested, up until 1 year after vaccination. Blood samples will be used to assess short- and long-term immunological effects of immunization. Evaluations will include vaccine antibody titers. Additional evaluations may include peripheral immune cell phenotyping, RNA sequencing (RNA-seq) of whole blood and defined peripheral blood cell subsets, and measurement of serum proteins and antibodies. Subjects may optionally provide stool samples at some visits for exploratory microbiome assessment. Additionally, subjects may optionally continue study participation annually through the 2023-24 influenza season.

The goal of this protocol is to use the collective information gathered across all healthy volunteers to understand how the immune system works as a whole.

1 Background Information and Scientific Rationale

1.1 Background Information

1.1.1 What is systems immunology?

Systems immunology is a field of research aimed to identify and understand how the different components of the immune system work together in a coordinated manner to achieve its functions, such as protecting against pathogens and mounting effective responses after vaccination. Although we have substantial information at the level of individual molecules and processes of the immune system that operate in isolation or as a part of smaller functional units, a significant gap in knowledge exists regarding how the different parts of the immune system work together as a whole.

Efforts to fully characterize the immune system have been limited due to 1) challenges in generating sufficient data to measure the diverse functions of the immune system, and 2) a lack of computational tools that combine all that data to create models of how the immune system works. Over the past decade, significant advances have been made in the volume and type of scientific data that can now be generated in both cell lines and living organisms, as well as advances in computational modeling techniques. By using these new modeling techniques to combine multiple types of data, we can build a more complete picture of the immune system than was previously possible.

1.1.2 Systems immunology applied to vaccines

Certain functions of the immune system are revealed only when the immune system is challenged. For example, in response to infection by Gram-negative bacteria, the Toll-like receptor 4 pathway is activated by bacterial lipopolysaccharide, a structural component of the Gram-negative bacterium outer wall, to produce inflammatory cytokines. A systems immunology approach has previously revealed important biological insights on the challenged immune system, such as the observation that chronic cytomegalovirus (CMV) infection is associated with both broad changes in numerous immune cell parameters in healthy individuals at baseline, as well as more robust flu vaccine responses in healthy young individuals.^{1,2}

Similarly, specific immune system pathways are activated following vaccination. When a person is vaccinated, a coordinated response results: activation and interaction of distinct innate and adaptive immune cell populations and pathways, culminating in the formation of germinal centers from which antibody-producing plasma cells and memory B cells derive. By taking measurements at various time points before and after vaccination, we can build a comprehensive picture of how the immune system responds to a vaccine challenge.

The seasonal influenza vaccination provides an excellent model of coordinated immune activity involving innate and adaptive responses, as demonstrated previously in a study conducted at the Center for Human Immunology (CHI) at the NIH (protocol 09-H-0239). This study employed the sampling strategy described above to capture the immune response to seasonal influenza vaccine in 63 healthy NIH employees. Multiple types of data from the blood were collected over numerous time points, and these data were combined using computational modeling to create a detailed picture of how the immune system responds to influenza vaccine. Among the key findings in this study were: 1) baseline immune status and early responses (days 1 and 7 post-vaccination) were highly variable between healthy subjects, and 2) several parameters (such as certain B-cell subsets) were both stable over time and predictive of the magnitude of antibody response to the vaccine (Figure 1).³

[figure not shown]

Figure 1. CHI study of influenza vaccination. Sixty-three healthy individuals had various blood measurements before and after vaccination with the seasonal influenza vaccine. Notable findings include: 1) an increase in innate immune cells (such as monocytes and activated CD4⁺ T-cells) in the days immediately after vaccination, 2) an increase in antibody-producing B cells (plasmablasts) 7 days after vaccination, and 3) several cell subsets (such as certain B-cell subsets) that are both stable in the time period before and after vaccination and predictive of the magnitude of antibody response to the vaccine.

This systems immunology approach has revealed important biological insights about the response to influenza vaccination.^{2,3} Additionally, this approach can illuminate interactions between acute infections and the acquired immunity that vaccines provide. Recently, it has been recognized that acute infections can have profound and persistent effects on the immune system. For example, measles infection frequently results in prolonged depletion of memory B cells and reduction in protective antibodies to previous infections and vaccinations, thus rendering patients at prolonged risk of infection from other organisms after measles recovery.^{4,5} It is possible that other infections, including infection with SARS-CoV-2, may also affect immunological memory, response to past and future vaccinations, and other long-term immunological phenomena. In light of the recent SARS-CoV-2 pandemic, the long-term immunological effects of SARS-CoV-2 infection have become a question of public health importance.

1.2 Scientific Rationale

The previous CHI study was conducted between 2009-2011. Since that time, there have been numerous technological and scientific advances that merit a follow-up study with more comprehensive sampling. The specific motivations are the following:

1. The previous CHI study included a day 70 time point as the most distal from the time of vaccination. We will add additional time points to examine the resolution of immune response following vaccination and antibody durability (beyond day 70).
2. New technologies such as mass cytometry (cytometry by time of flight, CyTOF) and cellular indexing of transcriptomes and epitopes by sequencing (CITE-seq) will permit us to interrogate cellular responses in detail. For example, CyTOF can simultaneously characterize more than 40 intracellular and extracellular proteins.⁶ CITE-seq is a technology that combines the power of extracellular marker detection with single-cell sequencing, allowing for single-cell gene expression to be linked to the specific cell (as defined by extracellular protein markers) from which the sequence originated.⁷
3. By allowing for sampling across several influenza seasons, we will be able to monitor for multi-season responses, ideally in the same individuals. Specific influenza vaccine strains are often repeated over sequential vaccine seasons; how this affects the immune response to subsequent vaccinations with the same influenza vaccine strain is not well understood.
4. Future studies of other vaccines (e.g., human papillomavirus vaccine) using the same systems immunology approaches would be able to use the data from this influenza vaccine study as a comparison.
5. This study is a unique opportunity to evaluate the potential effects of prior SARS-CoV-2 infection on the immune response to the seasonal influenza vaccine in healthy individuals.

These new goals are particularly important in light of the incompletely understood response to seasonal influenza vaccine and the importance of efforts aimed toward a universal influenza vaccine. The goal of this protocol is not to compare the immune response to the influenza vaccine between groups of healthy volunteers, but rather to measure and collectively evaluate numerous biological parameters (to include immune cell counts and whole blood gene expression) across all healthy volunteers in our study to understand how the immune system works as a whole. This systems immunology approach has previously revealed important biological insights, such as the previously mentioned observation that chronic CMV infection is associated with both broad immunological changes and response to the seasonal flu vaccine.¹ It has also helped shed light on the molecular drivers of immune aging,^{8,9} and the immunological responses to infectious diseases such as malaria.⁸ We aim to employ new technologies to study the immune response to the seasonal influenza vaccine over time (and seasons) in healthy volunteers. We hypothesize that these technologies, combined with a longer follow-up period

than previously employed, will allow us to better understand the molecular and cellular components of the immune system that together orchestrate protective vaccine responses.

2 Study Objectives

2.1 Primary Objective

Identify baseline correlates of immune response to the seasonal influenza vaccine in healthy individuals

2.2 Secondary Objectives

- Validate the findings of prior study 09-H-0239, specifically the relationship between cell populations and/or gene transcripts at baseline and after vaccination that correlate with vaccine immune response
- Evaluate the effect of prior SARS-CoV-2 infection on the antibody response to the seasonal influenza vaccine in healthy volunteers

2.3 Exploratory Objectives

Assess the immune responses over time and across seasons of healthy volunteers to influenza vaccination, including the relationship between this response and existing immunity to specific influenza vaccine strains, repeated immunization with the same vaccine strain, and African American (AA) race by evaluating a large number of biological parameters

3 Study Design

3.1 Description of the Study Design

This is a prospective, open-label, exploratory study to evaluate the baseline immune state and post-vaccination immune responses of healthy volunteers to the seasonal influenza vaccine. The study vaccine is approved and indicated by the US Food and Drug Administration (FDA) for active immunization for the prevention of influenza disease caused by influenza virus subtypes A and B. Blood samples will be collected at various timepoints before and up to 100 days after vaccination to explore short- and long-term immunological effects of immunization. Blood may also be collected at optional monthly study visits up until 1 year after vaccination. Subjects may optionally provide stool samples on days -7, 0, 28, and 100.

Subjects will remain on study and may optionally repeat study visits (including vaccination) annually through the 2023-24 influenza season, with final study follow-up up to 1 year after vaccination. Sampling individual subjects across several influenza seasons will allow us to monitor for multi-season responses.

Blood will be evaluated to characterize immune response parameters, primarily changes in antibody titers following vaccination. These evaluations will be used to assess expected response to the vaccination in order to identify baseline and early response correlates of vaccination responses (e.g., by searching among the many parameters we will measure, as listed in section 7.2). Other important immune response parameters include the frequency of peripheral monocytes and interferon transcriptomic signatures (past studies suggest both can be detected in the blood on day 1 following influenza vaccination), as well as the frequency of plasmablast and certain CD4⁺ T-cell subsets (detectable around day 7 in past studies with influenza vaccination). In this study, these parameters should be captured exactly on days 1 and 7, as the earlier CHI study of influenza vaccination demonstrated that measuring these on the specified days will minimize variability and maximize detection of biologically important signals.³ Additional research evaluations may include flow cytometry and transcriptome and genetic analyses.

In year 2 of this protocol, enrollment will be enriched according to history of SARS-CoV-2 infection. We will enroll up to 120 subjects by consecutive sampling in the following cohorts:

- Up to n=40 subjects with no history of SARS-CoV-2 infection, as determined by a negative antibody test at screening.
- Up to n=40 subjects with confirmed symptomatic SARS-CoV-2 infection, as determined by a documented positive polymerase chain reaction (PCR) test, and a positive antibody test at screening.
- Up to n=40 subjects with confirmed SARS-CoV-2 antibodies at screening or from an FDA-approved test as documented by the subject but with no history of symptoms.

This design will allow comparison between cohorts to explore the long-term immunological effects of SARS-CoV-2 infection. Recruitment in year 2 will be targeted toward these groups, and enrollment for each cohort will be stopped when its sample size is achieved for the year.

Because the vaccine response to the seasonal influenza vaccine in AA people has only started to be explored,¹⁰ we will recruit up to 10 AA subjects (of the 40) for each group described above in order to evaluate the relationship between AA race and vaccine responses in each of the three cohorts above.

Because obesity is associated with decreased vaccine responsiveness,¹¹ we will exclude individuals with a body mass index (BMI) ≥ 30 .

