6.1 Screening (day -30 to -7)

In the first year of participation, screening will include an in-person health/medication history and physical exam (including height and weight measurement for BMI) as well as the evaluations listed below. For optional participation in subsequent influenza seasons, screening will have the same evaluations but an electronic REDCap health history and medication questionnaire instead of an in-person history/physical, and subjects will be asked their height and weight to estimate BMI. For individuals who report a history of SARS-CoV-2 infection, we will also review COVID-19 symptoms and/or documentation of SARS-CoV-2 testing (from the NIH or outside since December 2019).

The following evaluations will be conducted at the screening visit:

- Urine or serum pregnancy test for women of childbearing potential.
- Blood draw for the following screening tests:
 - CBC with differential.
 - Lymphocyte phenotyping with TBNK.
 - Acute care, mineral, and hepatic panels.
 - Anti-CMV IgG and IgM antibody and anti-EBV antibody panel.
 - Anti-HIV 1/2 antibody, antibody to hepatitis B surface antigen, and anti-hepatitis C virus antibody.
 - SARS-CoV-2 serum antibody test for individuals who do not provide documentation of a positive FDA-approved antibody test result (since December 2019).
 - If an individual with a documented positive SARS-CoV-2 PCR test result is tested for antibodies at screening and the result is negative, antibody testing will be repeated (possibly with a different FDA-approved test). If the second antibody test is negative, the individual will only be eligible to enroll in the cohort with no history of SARS-CoV-2 infection.

If any of these evaluations have been conducted on another protocol at the NIH within the previous 30 days, then they will not be repeated, and those results will be used to determine eligibility on this study. The exception is the pregnancy test, which must be done at the NIH within the previous 2 days. Screening labs conducted under this protocol may be repeated at the discretion of the PI within 30 days.

If the results of any screening tests are consistent with a previously unknown health condition or other incidental findings, then the subject will be informed of the results. The results will also be provided to the subject's primary physician if requested. If the subject does not have a primary

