7.2 Laboratory Evaluations

Pre- and post-vaccination whole blood samples will be processed to isolate serum, PBMCs, RNA, and TBNK cells, which will be used for the following research evaluations:

- Antibody titers on serum.
- CBC with differential.
- Lymphocyte phenotyping (TBNK flow cytometry performed by the NIH CC).
- Whole blood transcriptome as analyzed by RNA-seq from stabilized RNA (e.g., via Tempus or PAXgene tubes).

Additional research evaluations to evaluate a large number of parameters may include but are not limited to the following:

- Flow cytometry on whole blood and/or immune cell subsets.
- Cellular transcriptional activity in immune cell subsets as analyzed by RNA-seq and/or microarrays.
- Quantification of gene expression (transcriptome) of PBMCs with RNA-seq and/or microarrays.
- Characterization of chromatin accessibility and promoter/enhancer landscapes in immune cell subsets with ATAC-seq and/or other techniques.
- Targeted genetic analyses including genotyping of specific regions of the genome (e.g., human leukocyte antigen and single nucleotide polymorphism typing), if not already performed on another protocol.
- Measurement of relative abundance of serum proteins with SomaLogic's SOMAscan assay or other assays.
- Serum antibody titers.
- Serum SARS-CoV-2 antibody testing using the Roche Elecsys[®] Anti-SARS-CoV-2 antibody test (under Emergency Use Authorization), which is classified as a Non-Significant Risk device because it does not meet any of the following definitions of a Significant Risk Device under 21 CFR 812.3(m):
 - Is intended as an implant and presents a potential for serious risk to the health, safety, or welfare of a subject;
 - Is purported or represented to be for use supporting or sustaining human life and presents a potential for serious risk to the health, safety, or welfare of a subject;
 - Is for a use of substantial importance in diagnosing, curing, mitigating, or treating disease, or otherwise preventing impairment of human health and presents a potential for serious risk to the health, safety, or welfare of a subject; or
 - Otherwise presents a potential for serious risk to the health, safety, or welfare of a subject.

The use of the Roche Elecsys[®] Anti-SARS-CoV-2 antibody test as a Non-Significant Risk device will follow the abbreviated requirements under 21 CFR 812.2(b)(1).

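### The asymptomatic SARS-CoV-2 cohort rests on one positive antibody result that need not be repeated, while the symptomatic cohort needs PCR and antibody, so false positives would dilute one cohort's contrast and largely spare the other's.

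*Combined protocol and SAP*

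**What the plan says.** Section 3.1 sets up three year-2 cohorts of up to 40 and closes each one when it is full.

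- **Uninfected:** "no history of SARS-CoV-2 infection, as determined by a negative antibody test at screening".
- **Symptomatic:** "documented positive polymerase chain reaction (PCR) test, and a positive antibody test at screening", so two concordant markers.
- **Asymptomatic:** "confirmed SARS-CoV-2 antibodies at screening or from an FDA-approved test as documented by the subject but with no history of symptoms". The text uses the word confirmed but defines no confirmation step.

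Section 6.1 limits the study's own antibody test to some entrants: "SARS-CoV-2 serum antibody test for individuals who do not provide documentation of a positive FDA-approved antibody test result". A documented positive dating back as far as December 2019 therefore stands in for it. The only mandatory repeat concerns a person with a documented positive PCR who is "tested for antibodies at screening and the result is negative, antibody testing will be repeated (possibly with a different FDA-approved test"). There is no matching rule for a positive result.

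Section 7.2 lists "Serum SARS-CoV-2 antibody testing using the Roche Elecsys" assay among evaluations that may be done and gives it no role in confirming cohort membership. Section 3.2.2 makes the titer difference between previously infected and uninfected subjects a secondary endpoint. Section 15.3 compares the three cohorts as enrolled, with no analysis that allows for misclassification.

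**The concern.** The repeat rule in 6.1 accepts that a single antibody result can be wrong, but it guards only against a false negative. A lone positive in a person with neither symptoms nor a PCR result is where prior probability tends to be low, and so where one test is least reliable.

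A false positive is an uninfected person counted as infected. In the symptomatic cohort it would take an error on both PCR and antibody; in the asymptomatic cohort one error is enough. Misclassification therefore differs between the two infected cohorts by design. The asymptomatic contrast would shrink while the symptomatic contrast stayed nearly intact, and a reader could take the gap for biology. Because each cohort closes at 40, every false positive also takes the place of a truly infected subject.

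**Working it through.** **1. The plan's own power figure.** Section 15.2 and Table 2 give 0.85 at N = 170 (effective n = 153) for a biomarker slope, Bonferroni-adjusted over 50 comparisons. Inputs: slope 0.29, var(R) = 2.09, var(X) = 3.03, two-sided alpha 0.05/50 = 0.001, critical value 3.291.

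- Mean of the Wald statistic = 0.29 / sqrt(2.09 / (152 × 3.03)) = 4.305.
- Power = Φ(4.305 − 3.291) = 0.845, which matches.

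This figure concerns the primary analysis. The plan states no effect size or power for the SARS-CoV-2 cohort comparison, and no assay accuracy or seroprevalence. Everything below rests on assumptions.

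**2. False positives with one test.** Assumed: sensitivity 95%; specificity 98%, 99%, 99.5% or 99.8%; true seropositivity among symptom-free people tested of 1%, 2%, 5% or 10%.

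PPV = prev × sens / [prev × sens + (1 − prev) × (1 − spec)]. Expected false positives of 40 = 40 × (1 − PPV).

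Example at 5% and 99%: 0.0475 / (0.0475 + 0.0095) = 0.833, so 40 × 0.167 = 6.7.

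| Specificity | 1% | 2% | 5% | 10% |
|---|---|---|---|---|
| 98% | 0.32 (27.0) | 0.49 (20.3) | 0.71 (11.4) | 0.84 (6.4) |
| 99% | 0.49 (20.4) | 0.66 (13.6) | 0.83 (6.7) | 0.91 (3.5) |
| 99.5% | 0.66 (13.7) | 0.80 (8.2) | 0.91 (3.6) | 0.95 (1.8) |
| 99.8% | 0.83 (6.9) | 0.91 (3.7) | 0.96 (1.5) | 0.98 (0.7) |

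Cells show PPV, with expected false positives of 40 in brackets; columns are seropositivity. At 99.5% and 10% the share is 1.8/40 = 4.5%.

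**3. Dilution.** If false positives respond like uninfected people, the expected observed difference is PPV × true difference. As an illustration, take 40 per cohort, SD 1, two-sided alpha 0.05, and a true difference of 0.627 SD, chosen because it gives 80% power without misclassification. Power = Φ(0.627 × PPV / sqrt(2/40) − 1.96).

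| PPV | Expected difference (SD) | Power | n per cohort to restore 80% |
|---|---|---|---|
| 1.00 | 0.63 | 80% | 40 |
| 0.95 | 0.60 | 76% | 45 |
| 0.90 | 0.56 | 71% | 50 |
| 0.80 | 0.50 | 61% | 63 |
| 0.70 | 0.44 | 50% | 82 |
| 0.50 | 0.31 | 29% | 160 |

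**4. Two concordant positives.** With independent errors and equal accuracy, replace sens by sens² and (1 − spec) by (1 − spec)². The worst corner (1%, 98%) gives 0.009025 / (0.009025 + 0.99 × 0.0004) = 0.958; every other cell is higher. Errors shared between the assays would lower these values.

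**The case against.** **Discretionary repeats.** A reader might infer that a positive is never rechecked. The documents do not support that. Section 6.1 lets the investigator repeat screening labs within 30 days, and 7.2 allows the Roche test on study blood. Appendix A also marks the antibody test at screening without the waiver footnote that the other screening bloods carry, which sits awkwardly with 6.1. What stands is that no repeat is required and none is tied to cohort membership.

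**Enriched recruitment.** Year-2 enrollment is enriched by infection history (3.1), and 4.1 draws on protocols studying SARS-CoV-2 infection, antibodies or exposure, with review of existing results. The 1-2% columns may be too pessimistic. This stands as a limit on size. It does not close the gap, because general volunteer sources are also used and no minimum prior probability is set.

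**Exploratory purpose.** The study is hypothesis-generating, and the power table in step 3 uses a difference the plan never states. That is fair: the power figures illustrate attenuation and do not describe a planned test that fails. The attenuation does not depend on the chosen difference.

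**Waned antibody.** Section 6.1 itself foresees PCR-positive people who test antibody-negative, and an outside positive may be old. A negative second assay cannot separate a false positive from a true infection whose antibody has waned. Confirmation as an entry condition could drop true infections and favour stronger or more recent seropositives. This argues against changing the entry criteria, but not against a second assay with both analyses reported.

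**Conclusion.** The unequal confirmation is plain in the text: one positive antibody result for the asymptomatic cohort, two concordant markers for the symptomatic cohort, and no required repeat of a positive. The direction of the resulting bias is clear if false positives respond like uninfected people. The asymptomatic-versus-uninfected difference moves toward zero in proportion to PPV, and the symptomatic contrast is largely spared.

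The size is not established. Over the assumed ranges it runs from under 1 to about 27 false positives of 40, and dilution is minor at the favourable end. A reader might infer that a material share of this cohort is falsely positive, or that a symptomatic-versus-asymptomatic difference would be purely an artifact. The documents support neither; such a difference could partly reflect unequal confirmation. The point touches one arm of one secondary endpoint and leaves the primary objective alone. It is worth acting on because the remedy is cheap.

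**What to change.** Leave the entry criteria in 3.1 unchanged.

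- **Sections 6.1 and 7.2:** for every asymptomatic-cohort subject, run a second, different antibody assay on screening or day -7 serum already collected. Use the listed Roche test for those who enter on outside documentation, and another FDA-approved or authorised assay if Roche was the first.
- **Section 15.3:** report the asymptomatic-versus-uninfected comparison for all entrants and for confirmed positives only. State in advance that any claim that asymptomatic infection has a different effect, or none, requires the two results to agree.

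The cost is one extra assay on about 40 stored samples and a few sentences of protocol text. The confirmed-only set will be smaller and may leave out true infections whose antibody has waned, which is why the all-entrant result is kept beside it.
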